3.1.3 Study Schema

3.1.4 Dose Limiting Toxicity

A dose-limiting toxicity (DLT) is defined as a clinically significant adverse event assessed as unrelated to tumor progression, intercurrent illness or concomitant medications and meets any of the criteria below. Any DLT must be a toxicity considered at least possibly related to selinexor and the acute effects thereof.

- Any grade 3 or 4 toxicity as per CTCAE Criteria Version 5.0 during treatment and within 30 days after completion of RT
- Any grade 3 or 4 toxicity as per Section **14.1.2.** RTOG acute morbidity during treatment and within 30 days after completion of RT
- Any toxicity at least possibly related to selinexor that causes a patient to miss consecutive radiation or temozolomide doses for 5 days.

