3.1.5 Dose Escalation

This study will use a 3+3 design, with 3-6 patients enrolled per dose level to define maximum tolerated dose (MTD). The MTD is the dose level at which no more than 1 of up to 6 patients experience DLT within 1 month of completion of treatment, and the dose below that at which at least 2 (of ≤6) patients have DLT as a result of selinexor/RT/temozolomide. If a patient did not experience DLT and did not finish treatment, he or she will not be evaluable for toxicity and will be replaced in the dose level. Enrollment to a dose level would stop if 2 or more patients had a DLT.

The number of patients may be increased to 9 total patients at the MTD (provided no DLT) with a maximum of 21 evaluable patients enrolled and the minimum evaluable patients required will be 15. The once weekly dosing schedule was based on the results of the KCP-330-004 study Arm D. The twice weekly dose of 60mg is from KCP-330-004 Arm C.

| Dose Escalation Schedule of Selinexor | |
|--|--|
| Dose Level | |
| Level -1 | 80 mg on weeks 1, 4 |
| Level 1 | 80 mg on weeks 1, 2, 4, 5 |
| Level 2 | 60 mg twice a week on weeks 1, 2, 4, 5 |
| Level 3 | 60 mg twice a week, weeks 1-6 |

All patients will receive 2Gy daily RT plus 75mg/m² temozolomide.

Dose escalation will follow the rules outlined in the Table below.

| Number of Patients with DLT at a Given Dose Level | Escalation Decision Rule |
|---|--|
| 0 out of 3 | Enter up to 3 patients at the next dose level |
| ≥ 2 | Dose escalation will be stopped. This dose level will be declared the maximally administered dose (highest dose administered). Up to three (3) additional patients will be entered at the next lowest dose level if only 3 patients were treated previously at that dose. |
| 1 out of 3 | Enter up to 3 more patients at this dose level. 
• If 0 of these 3 patients experience DLT, proceed to the next dose level.• If 1 or more of this group suffer DLT, then dose escalation is stopped, and this dose is declared the maximally administered dose. Up to three (3) additional patients will be entered at the next lowest dose level if only 3 patients were treated previously at that dose. |
| ≤ 1 out of 6 at highest dose level below the maximally administered dose | This is the MTD and is generally the recommended phase 2 dose. At least 6 patients must be entered at the recommended phase 2 dose. |

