3.8 CRITERIA FOR REMOVAL FROM PROTOCOL THERAPY AND OFF STUDY CRITERIA

Prior to removal from study, effort must be made to have all subjects complete a safety visit approximately 30 days following the last dose of study therapy.

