10 STATISTICAL CONSIDERATIONS

10.1 STATISTICAL HYPOTHESIS

10.1.1 Primary Endpoint

Define the maximum tolerated dose (MTD) of Selinexor given concurrently with radiation and temozolomide. Assessment of toxicities for dose escalation will occur for 30 days following the completion of RT.

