10.2 SAMPLE SIZE DETERMINATION

The primary objective of this trial is to determine the safety, toxicity profile, DLT and maximum tolerated dose (MTD) of Selinexor given concurrently alongside temozolomide and radiation in patients with newly diagnosed glioblastoma patients. There are 3 planned dose levels for this trial that will enroll 1 to 6 patients each using the 3+3 design to define the MTD. The MTD will be based on the assessment of DLT within one month following the irradiation, and will be defined as the dose level at which less than one-third of patients (0/3 or 0-1/6 patients) treated at that dose level experience a DLT, with the next higher dose level demonstrating a one-third or greater number of patients ($\geq 2/3$ or $\geq 2/6$ patients) having DLT. If a patient did not experience DLT and did not finish therapy, he or she will not be evaluable for determination of the MTD

and will be replaced in the dose level. An additional 3 to 6 patients will be enrolled at the MTD, so that a total of 9 patients will be treated at this dose to better characterize the clinical activity of this combination in this patient population. Thus, if all 3 dose levels are evaluated (6 patients per dose level with 9 total patients at the MTD or maximum administered dose), a maximum of 21 evaluable patients will be enrolled. Similarly, if all dose levels are evaluated, the minimum number of evaluable patients required will be 15. To compensate for inevaluable patients, an additional 3 patients may be enrolled. Thus, a maximal of 24 patients are targeted for this study. It is expected that accrual can be completed in 24 months.

Using this dose escalation scheme, the probability of escalating to the next dose level, based on the true rate of DLT at the current dose, is given by the following table (each group will be considered independently of the other):

| True rate of DLT at a given dose | 10% | 20% | 30% | 40% | 50% | 60% |
|----------------------------------|-----|-----|-----|-----|-----|-----|
| Probability of escalating | .91 | .71 | .49 | .31 | .17 | .08 |

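### The DLT window is anchored inconsistently to the end of RT, and no rule says when it closes for a patient whose RT stops early

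*Combined protocol and SAP*

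**What the plan says.** Section 3.1.4 has two graded DLT criteria. The CTCAE one is "Any grade 3 or 4 toxicity as per CTCAE Criteria Version 5.0 during treatment and within 30 days after completion of RT". The RTOG one covers "RTOG acute morbidity during treatment and within 30 days after completion of RT". A third criterion has no time limit: toxicity at least possibly related to selinexor that makes a patient miss RT or temozolomide for 5 consecutive days.

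The window appears three more times, each worded differently:

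- Section 3.1.5, in the MTD definition, counts patients who "experience DLT within 1 month of completion of treatment".
- Section 10.1.1: "Assessment of toxicities for dose escalation will occur for 30 days following the completion of RT".
- Section 10.2: "The MTD will be based on the assessment of DLT within one month following the irradiation".

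On replacement, section 3.1.5 says "If a patient did not experience DLT and did not finish treatment, he or she will not be evaluable for toxicity and will be replaced", and section 10.2 repeats the rule for MTD evaluability. Section 10.3.1 instead makes every patient evaluable for toxicity from the first selinexor treatment. Section 3.8.1 lists completing 6 weeks of RT as one way off protocol therapy, separate from progression, participant request, unacceptable toxicity, investigator discretion and pregnancy.

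**The concern.** For a patient who finishes RT, the four wordings close at about the same time, because concurrent temozolomide ends with RT. They diverge only for a patient who stops early.

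Take a patient who leaves RT at their own request and has a first selinexor-related grade 3 event 10 days after the last fraction and last study drug dose. Read literally, section 3.1.4 no longer has this patient on treatment, and RT was never completed, so neither graded period contains the event. The third criterion does not apply either, because no selinexor toxicity caused the missed doses. The patient then counts as having had no DLT and not having finished, and is replaced.

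The MTD is the primary endpoint and rests on 3 to 6 patients per level. One patient reclassified in this way can change the escalation decision, and two people applying the text in good faith could classify the same patient differently.

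**Working it through.** **1. The wordings applied to an early stopper**

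| Section | Window ends 30 days or one month after | Early stopper's late event counted? |
|---|---|---|
| 3.1.4 (operative definition) | RT is completed | No, read literally |
| 3.1.5 | treatment is completed | Unclear |
| 10.1.1 | RT is completed | No, read literally |
| 10.2 | the irradiation | Yes, if read as from the last fraction |

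The evaluability rules conflict too: 3.1.5 declares such a patient not evaluable for toxicity, while 10.3.1 declares everyone evaluable from first selinexor.

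**2. The plan's own figure**

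The 3+3 rule escalates on 0/3, or on 1/3 followed by 0/3. With true DLT rate p:

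P(escalate) = (1−p)³ + 3p(1−p)²·(1−p)³

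For p = 10%, 20%, 30%, 40%, 50% and 60% this gives 0.906, 0.709, 0.494, 0.309, 0.172 and 0.082. The table in 10.2 has .91, .71, .49, .31, .17 and .08, so it reproduces.

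**3. Effect on one cohort**

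If one of three patients has a DLT, 3.1.5 adds up to 3 more patients at that level. If that patient is instead replaced and the replacement has no DLT, the result reads 0/3 and the next level opens. In the same way, 2/6 (escalation stops) can become 1/6.

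**4. Effect on the counted rate**

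Let s be the share of DLT patients whose event is lost through the gap, and f the share of non-DLT patients who stop early and are replaced. The documents give neither. The rate among evaluable patients is

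p′ = p(1−s) / [p(1−s) + (1−p)(1−f)]

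The counted odds are p(1−s)/[(1−p)(1−f)] under the literal text and p/[(1−p)(1−f)] if the event is counted. Their ratio is 1−s for every f. Relative to counting the event, the gap therefore always lowers the counted rate.

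Relative to the 10.2 table the picture differs. If s = f, the terms cancel and p′ = p. The range below assumes that early stopping is unrelated to DLT, and that every early stopper's DLT falls after the stop and is lost (s = f):

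| s = f (assumed) | p = 30%: event counted → lost | p = 40%: event counted → lost |
|---|---|---|
| 5% | 0.472 → 0.494 | 0.290 → 0.309 |
| 10% | 0.449 → 0.494 | 0.269 → 0.309 |
| 20% | 0.399 → 0.494 | 0.228 → 0.309 |

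Example at p = 30%, f = 10%. Event counted: 0.30/(0.30 + 0.70×0.90) = 0.30/0.93 = 32.3%, so P(escalate) = 0.449. Event lost with s = 10%: 0.27/(0.27 + 0.63) = 30.0%, so P(escalate) = 0.494.

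Under these assumptions the gap adds about 2 to 10 points at p = 30% compared with counting the event, but does not push the chance above the plan's own 0.49.

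**The case against.** **The text allows a window for early stoppers.** Section 10.2 does not mention completion. Section 3.2.2 has temozolomide continue until radiation is completed and then stop, which works for an early stopper only if completion means the end of RT as given. The calendar's follow-up note is similar. This stands: a reader might infer from 3.1.4 that early stoppers certainly have no post-treatment window, and the documents do not support that certainty. But 3.1.4 is the operative definition, and 3.8.1 distinguishes completing 6 weeks of RT from the other exits. The ambiguity remains.

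**The gap is narrow.** This also largely stands. A selinexor toxicity that causes 5 consecutive missed days is already a DLT whether or not RT finishes. What remains is a stop for another reason, followed by a first grade 3 or 4 event at least possibly related to selinexor and not due to progression, intercurrent illness or concomitant medication.

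**The event is not lost to safety data.** Correct. Section 6.1 records adverse events through 30 days after the last study drug, and 7.4.1 has weekly team review. What can be lost is its count as a DLT.

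**A large inflation is tempting but unsupported.** Setting f = 0 and s = 10% to 50% at p = 30%, a reader might infer that the chance of escalating rises from 0.49 to between 0.54 and 0.76. That assumes only DLT patients are replaced, whereas the rule also replaces non-DLT early stoppers. With s = f = 12.5% (assumed), the counted rate stays at 30.0% and P(escalate) at 0.49. If only half of the early stoppers' DLTs are lost (s = 6.25%), they are 31.5% and 0.46. Also, s = 50% at p = 30% would mean that 15% of all patients are lost DLT cases, more than the whole allowance of 3 in 24 (12.5%). That allowance is not a forecast either: "To compensate for inevaluable patients, an additional 3 patients may be enrolled" sets a permitted number, not an expected rate.

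**Section 10.1.1 might be read as leaving out events during RT.** The documents do not support this: 3.1.4 expressly includes the treatment period, and the calendar schedules toxicity assessment during radiation.

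**Conclusion.** The concern holds as an inconsistent and incomplete definition of the primary endpoint's observation window. No section says what applies when RT stops early. On the literal wording of 3.1.4, a first selinexor-related grade 3 or 4 event after an early stop for another reason is not a DLT and the patient is replaced. On one reading of 10.2 the same event counts.

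The direction is certain only against the alternative of counting the event: the gap then lowers the DLT count and favours escalation. The size cannot be derived from the documents. The 2 to 10 points at a 30% true rate rest on assumed early-stop shares of 5% to 20%, on stopping being unrelated to DLT, and on every such DLT being lost. No rise above the 10.2 table can be claimed. The point still deserves an amendment, because a single reclassified patient can change a cohort's decision and the correction is cheap.

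**What to change.** Reconcile 3.1.4, 3.1.5, 10.1.1, 10.2 and 10.3.1 to one DLT window. It should run from the first protocol treatment to 30 days after the last RT fraction or last concurrent study drug dose actually given, whichever is later, whether or not the planned course was completed.

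In 3.1.5 and 10.2, add that a patient who did not finish is declared inevaluable for the MTD, and replaced, only once that window has closed without a DLT. In 10.3.1, separate the general toxicity population (everyone from first selinexor) from the set evaluable for the MTD.

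No new visit is needed. Section 3.8 already asks that patients "complete a safety visit approximately 30 days following the last dose of study therapy", and 6.1 collects adverse events for 30 days after the last study drug. The cost is the amendment itself and a delay of up to about 30 days before an early stopper is replaced.

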3.1.5 Dose Escalation

This study will use a 3+3 design, with 3-6 patients enrolled per dose level to define maximum tolerated dose (MTD). The MTD is the dose level at which no more than 1 of up to 6 patients experience DLT within 1 month of completion of treatment, and the dose below that at which at least 2 (of ≤6) patients have DLT as a result of selinexor/RT/temozolomide. If a patient did not experience DLT and did not finish treatment, he or she will not be evaluable for toxicity and will be replaced in the dose level. Enrollment to a dose level would stop if 2 or more patients had a DLT.

The number of patients may be increased to 9 total patients at the MTD (provided no DLT) with a maximum of 21 evaluable patients enrolled and the minimum evaluable patients required will be 15. The once weekly dosing schedule was based on the results of the KCP-330-004 study Arm D. The twice weekly dose of 60mg is from KCP-330-004 Arm C.

| Dose Escalation Schedule of Selinexor | |
|--|--|
| Dose Level | |
| Level -1 | 80 mg on weeks 1, 4 |
| Level 1 | 80 mg on weeks 1, 2, 4, 5 |
| Level 2 | 60 mg twice a week on weeks 1, 2, 4, 5 |
| Level 3 | 60 mg twice a week, weeks 1-6 |

All patients will receive 2Gy daily RT plus 75mg/m² temozolomide.

Dose escalation will follow the rules outlined in the Table below.

| Number of Patients with DLT at a Given Dose Level | Escalation Decision Rule |
|---|--|
| 0 out of 3 | Enter up to 3 patients at the next dose level |
| ≥ 2 | Dose escalation will be stopped. This dose level will be declared the maximally administered dose (highest dose administered). Up to three (3) additional patients will be entered at the next lowest dose level if only 3 patients were treated previously at that dose. |
| 1 out of 3 | Enter up to 3 more patients at this dose level. 
• If 0 of these 3 patients experience DLT, proceed to the next dose level.• If 1 or more of this group suffer DLT, then dose escalation is stopped, and this dose is declared the maximally administered dose. Up to three (3) additional patients will be entered at the next lowest dose level if only 3 patients were treated previously at that dose. |
| ≤ 1 out of 6 at highest dose level below the maximally administered dose | This is the MTD and is generally the recommended phase 2 dose. At least 6 patients must be entered at the recommended phase 2 dose. |

3.1.6 Study Stopping Rule

Accrual will be halted if there are ≥ 2 patients who miss consecutive doses of RT or temozolomide for 5 days that are possibly attributable to the selinexor treatment.

Prior to resumption of the study, PI will evaluate these events and determine the next course of action.

3.2 DRUG ADMINISTRATION

3.2.1 Selinexor

At dose level 1, Selinexor will be administered orally at an initial dose of 80 mg. The first dose will be given on day 2 of radiation and will thereafter be administered weekly on the second day of weekly radiation on weeks 1, 2, 4, and 5. If dose level 1 is tolerated, the Selinexor dose will be escalated to 60 mg twice a week on weeks 1, 2, 4, 5 given on Monday and Thursday. The third and final dose level will be 60 mg administered twice a week (on Monday and Thursday of radiation) for 6 weeks.

Prophylactic concomitant treatments with a 5-HT3 antagonist and olanzapine may be administered per section [4](#).

3.2.2 Temozolomide

Temozolomide will begin on the first day or evening prior of radiation and be administered orally daily at a dose of 75 mg/m^2 during the radiation treatment. Temozolomide will continue until the completion of radiation and then will be stopped.

Beginning 1-month post-RT, the adjuvant temozolomide will be given per standard of care.

3.2.2.1 CCR self – administered study drugs policy

All oral self-administered study drug will be properly accounted for, handled, and disposed in accordance with existing federal regulations and principles of Good Clinical Practice. All oral study drugs will be recorded in the patient diary found in [Appendix H](#) or [Appendix I](#). This will be used as a memory aide for subjects. The clinical research team will maintain the primary source record. Subjects should be asked to bring the diary as well as unused study drug and empty containers with them at each study visit. If a subject goes off study while at home, the research nurse will ensure and document the return of the unused oral study drug from the participant. Unused study drug will be disposed and destroyed per CC pharmacy SOPs.

3.3 DOSE MODIFICATIONS

3.3.1 Radiation Therapy

Modifications to the radiation treatment plan will be made at the discretion of the radiation oncologist. Ideally, radiation therapy will be delivered uninterrupted. Occasionally, deviations from this schedule may be required secondary to expected toxicity or life events.

3.3.2 Concurrent Systemic Agents

3.3.2.1 Selinexor

Supportive Care and Selinexor Dose Adjustment Guidelines for AEs related to Selinexor ^{a,b}

| Toxicity and Intensity | Supportive Care and Dose Adjustment Guidelines |
|---|--|
| Fatigue | |
| Grade 1 or Grade 2 lasting \leq 7 days | Maintain dose. Rule out other causes. If found to be anemic and symptomatic, consider transfusions for hemoglobin >8 g/dL (Grade <3). |
| Grade 2 lasting >7 days or Grade ≥ 3 | Rule out other causes. If found to be anemic and symptomatic, consider transfusions for hemoglobin >8 g/dL (Grade <3); transfusions usually indicated for hemoglobin <8 g/dL (Grade ≥ 3). Stop Selinexor. |
| Anorexia or Weight Loss | |
| Grade 1 weight loss or Grade 2 anorexia and weight loss | Maintain dose. Rule out other causes. Consider nutritional consultation and utilize nutritional supplements. Should consider olanzapine 2.5 mg to 5 mg once a day if the weight loss is rapid. |
| Grade 2 weight loss or Grade ≥ 3 anorexia and weight loss | Rule out other causes. Consider nutritional consultation and utilize nutritional supplements or consider appetite stimulants including olanzapine 2.5 mg to 5mg once a day. Stop Selinexor. |
| Nausea, Acute | |
| Grade 1 or 2 (If intolerable or persistent Grade 2 not responsive to supportive care follow guidelines for Grade 3) | Maintain dose. Rule out other causes. Utilize any additional anti-nausea needs to supplement breakthrough nausea |
| Grade 3 | Rule out other causes. Utilize additional anti-nausea meds to supplement the breakthrough nausea |

| Toxicity and Intensity | Supportive Care and Dose Adjustment Guidelines |
|---|--|
| | Stop Selinexor. |
| Hyponatremia | |
| Grade 1 (sodium levels <Normal to 130 mmol/L) | Maintain dose. Rule out other causes including drug (e.g. diuretics) effects. Be certain that reported sodium level is corrected for concurrent hyperglycemia (serum glucose >150mg/dL). Treat hyponatremia per institutional guidelines including dietary review. Consider addition of salt tablets to patient's diet. |

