^a For all Grade ≥ 3 hematological or non-hematological AEs that are NOT Selinexor or Temozolomide related, after consultation with the Medical Monitor and at the discretion of the Investigator, selinexor may be maintained

^b For all Selinexor-related AEs, if the below prescribed dose reductions/interruptions result in a stabilization of ≥ 4 weeks, a re-escalation may be considered after approval from the Medical Monitor.

All dose modifications should be based on the worst preceding toxicity.

Note: It is strongly encouraged that the Investigator dose reduces or interrupts one drug at a time for those AEs that are thought to have multifactorial causes.

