3.3.2.2 Temozolomide (TMZ)

3.3.2.2.1 During concomitant radiotherapy

A complete blood count should be obtained weekly. Adjustments to the dose of Temozolomide and Selinexor will be made at the direction of the PI or study chairperson.

| Toxicity and Intensity | Supportive Care and Dose Adjustment Guidelines |
|-------------------------------|--|
| Platelets | |
| >75k | Continue both drugs. |
| Grade 2, >50-75k | Hold TMZ Hold Selinexor Continue RT. Recheck CBC, when platelets >75k restart TMZ and selinexor |

| | |
|-----------------|---|
| Grade 3, 25-50k | Hold TMZ. Discontinue Selinexor. Continue RT. Recheck CBC, when platelets >75k restart TMZ |
| Grade 4, <25k | Hold TMZ Discontinue Selinexor Hold RT Recheck CBC, when platelets >50k restart RT When platelets >75 k restart TMZ |
| ANC | |
| >1.5 | Continue both drugs |
| Grade 2, >1-1.5 | Hold TMZ Hold Selinexor Continue RT Recheck CBC when ANC 1.5 restart TMZ and selinexor |
| Grade 3, 0.5-1 | Hold TMZ Discontinue Selinexor Continue RT Recheck CBC, when ANC >1.5 restart TMZ |
| Grade 4, <0.5 | Hold TMZ Discontinue Selinexor Continue RT Recheck CBC, when ANC >1,5 restart TMZ, |

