3.5 STUDY CALENDAR

| Procedure | Screening | Baseline ¹ | Radiation ² (every day up to 6 weeks) | Follow-up (Total 3 yrs) ^{8, 10} | | |
|--|-----------|-----------------------|---|--|--------------------------------|---------------------------------|
| | | | | 1 month | Every 2 months for 2 yrs | Every 3 months for 3rd yr |
| History & PE | X | X | | X | X | X |
| Karnofsky Performance | X | X | | X | X | X |
| Neurological function & Mental Status | X | X | | X | X | X |
| Vital signs incl Weight | X | X | X | X | X | X |
| Height | X | | | | | |
| Pathology review incl molecular CNS panel | X | | | | | |
| Treatment | | | | | | |
| On treatment visit (OTV) evaluation once per week | | | X | | | |
| Temozolomide (Daily) ³ | | | X | | | |
| Selinexor ⁴ | | | X | | | |
| Toxicity assessment ^{5, 9} | | | X | X | X | X |
| Labs (Please refer section 2.2.2 for details) | | | | | | |
| Hematology ^{6a} | X | X | X | X | X | X |
| Chemistries ^{6b} | X | X | X | X | X | X |
| Thyroid function tests | | X | | | | |
| Pregnancy Test (urine/serum) | X | X | | | | |
| Hepatitis A, B and C testing | X | | | | | |
| HIV testing | X | | | | | |
| Radiographic (Please refer section 2.4 for details) | | | | | | |
| MRI | X | X | | X | X | X |
| CT scans | | X | | | | |
| Questionnaires (Please refer section 3.4 for details) | | | | | | |
| QoL questionnaires per MDASI-BT (Appendix D) ⁷ | | X | X | X | X | X |
| PROMIS Depression, PROMIS Anxiety, and NeuroQoL (Appendix E) ⁷ | | X | X | X | X | X |
| PRO-CTCAE (Appendix F) ⁷ | | X | X | X | X | X |

¹ Tests done at screening do not need to be repeated on baseline (C1D1) if performed within 7 days prior to enrollment except physical exam, KPS, vital signs, neurological exam, performance and mental status, and urine pregnancy test. Screening laboratory evaluations do not need to be repeated if done within 14 days prior to enrollment.

- ² Patients will be treated with 2Gy daily RT plus 75mg/m² temozolomide for six weeks with Selinexor given once or twice a week depending on dose level.
- ³ Regarding temozolomide dosing details, please refer to section [**3.2.2**](#).
- ⁴ Administered per section [**3.1.5**](#).
- ⁵ Assessment of acute toxicity (CTCAE Version 5.0 and RTOG Acute Morbidity score. (see [**Appendix B**](#) and [**Appendix C**](#))
- ⁶ Laboratory evaluation weekly during radiation.
 - a. Complete blood count with differential and platelets, PT/INR, PTT

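### The selinexor dose table tells staff both to maintain and to stop the drug for grade 2 anorexia with grade 2 weight loss

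*Combined protocol and SAP*

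**What the plan says.** The anorexia and weight loss block of the table in section 3.3.2.1 has two rows.

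- **Maintain row.** Trigger: "Grade 1 weight loss or Grade 2 anorexia and weight loss". Action: "Maintain dose. Rule out other causes. Consider nutritional consultation and utilize nutritional supplements", with olanzapine to be considered if weight falls quickly.
- **Stop row.** The trigger opens "Grade 2 weight loss or Grade" and continues with anorexia of grade 3 or higher and weight loss. Action: nutritional support or appetite stimulants, and selinexor is stopped.

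A note under the table adds: "All dose modifications should be based on the worst preceding toxicity". Section 3.3.2.2.1 adds: "Adjustments to the dose of Temozolomide and Selinexor will be made at the direction of the PI or study chairperson". The study calendar (section 3.5) lists "On treatment visit (OTV) evaluation once per week". Under section 3.1.4, the first grade-based criterion for a dose-limiting toxicity (DLT) is "Any grade 3 or 4 toxicity as per CTCAE Criteria Version 5.0 during treatment and within 30 days after completion of RT".

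**The concern.** The maintain row names grade 2 anorexia with weight loss and sets no upper limit on the weight loss. The stop row names grade 2 weight loss and sets no condition on anorexia. Grade 2 for both events therefore satisfies both triggers, and the actions are opposite.

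At stake is consistent handling of the investigational drug in a patient who is losing weight. Both events are expected. Section 1.2.9 reports anorexia of any grade in 51.1% of patients in company-sponsored trials, and section 14.1.2.1 lists weight loss among effects seen in 10% or more. The table also reaches beyond itself, because section 3.8.1 makes unacceptable toxicity under section 3.3 a ground for removal from protocol therapy.

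**Working it through.** The plan gives no figure on this point, so there is none to reproduce. The check sets the two rows against every grade pair and then counts the doses that could be affected.

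**1. Grade pairs and readings.** Let *a* be the anorexia grade and *w* the weight-loss grade, each 0 to 3, with 3 standing for 3 or higher. Excluding (0,0) leaves 4 × 4 − 1 = 15 pairs. The first limb of each row is taken as written: *w* = 1 for maintain and *w* = 2 for stop. The second limb (anorexia and weight loss) can be read four ways:

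- (i) both events at the stated grade;
- (ii) anorexia at that grade with any weight loss;
- (iii) either event at that grade;
- (iv) anorexia at that grade, with the weight-loss grade carried over from the row's first limb.

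Four readings for each row give 4 × 4 = 16 combinations.

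**2. The pair (2,2).** The stop row is always met, because *w* = 2 is enough. The maintain row is met under (i), (ii) and (iii), and not under (iv).

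- Both rows: 3 × 4 = 12 of 16.
- Stop row only: 1 × 4 = 4 of 16, all using reading (iv) for the maintain row.
- Maintain row only: 0 of 16.

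**3. The pair (3,1).** The maintain row is always met, because *w* = 1 is enough. The stop row is met under (ii) and (iii), and not under (i) or (iv).

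- Both rows: 4 × 2 = 8 of 16.
- Maintain row only: 4 × 2 = 8 of 16.
- Stop row only: 0 of 16.

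**4. Does other text break the tie for (2,2)?** The note on worst preceding toxicity ranks toxicities, not rows. Here the worst grades are 2 and 2, which is the pair that sits in both rows. Section 3.3.2.2.1 says who decides, not which row applies.

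**5. Doses at stake.** The schedule in section 3.1.5 gives 4 weeks × 1 = 4 doses at level 1 and 4 weeks × 2 = 8 at level 2. Level 3 is "60 mg twice a week, weeks 1-6", so 6 × 2 = 12. The table shows the most doses that can remain after onset. The onset week is an assumption.

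| Onset after | Level 1 (of 4) | Level 2 (of 8) | Level 3 (of 12) |
|---|---|---|---|
| week 1 | 3 | 6 | 10 |
| week 2 | 2 | 4 | 8 |
| week 4 | 1 | 2 | 4 |
| week 5 | 0 | 0 | 2 |

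These are upper bounds. The number is 0 if another stop rule is met before the next dose.

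**The case against.** The strongest reply is that the intent can be recovered. Grade 2 weight loss alone already means stop, and it would be perverse to continue because grade 2 anorexia is added. The stop row is met in all 16 combinations, so the only doubt is whether a second row also applies. The worst-toxicity note can be taken to favour the stricter action. For grade 3 anorexia with grade 1 weight loss it points more clearly to the stop row, the only row in this block that names grade 3 or higher; a grade 3 event possibly related to selinexor would also be reviewed as a possible DLT. In practice there is one centre, the PI or study chairperson directs adjustments, and the research team discusses each patient weekly (section 7.4.1). The table is headed as guidelines.

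The counts of readings also deserve caution. They are not probabilities of misuse, and they mix different readings of the same construction in adjacent rows. With one reading used for both rows, four combinations remain: three give the overlap and one gives stop only. Reading (iii) is implausible for the maintain row, since it would put grade 2 weight loss alone in both rows. Without it, 3 × 4 = 12 combinations remain, with overlap in 2 × 4 = 8 and stop only in 4.

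Much of this stands as an argument that the effect is small and that a careful investigator would probably stop. It does not remove the contradiction. The separating reading depends on a grade 1 limit that the row does not contain, and no rule of precedence is written.

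**Conclusion.** The concern holds. As written, the table gives opposite instructions for one grade pair, and nothing else in the protocol settles it. That stopping is intended is an inference from the table's own cut at grade 2 weight loss.

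The consequence is limited. No patient count can be given: the documents do not report how often the pair occurs, and section 1.2.5 says significant weight loss had not been seen in clinical trials to date. Per affected patient, the doses at stake run from 0 to 10 of 12 at level 3 over the onset weeks shown, and a patient kept on drug can still meet a stop rule at a later weekly visit. Grade 2 is below the grade threshold for a DLT, so the DLT rules, escalation and sample size are unaffected. Whether stopping selinexor early counts as not finishing treatment, which under section 3.1.5 would lead to replacement of a patient without a DLT, is not stated, and nothing here rests on it.

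This should be corrected because it is a stopping instruction for the investigational drug in an operative safety table. It does not threaten the primary endpoint.

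**What to change.** Reword the two triggers:

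- **Maintain dose:** *Grade 1 weight loss with no more than Grade 2 anorexia, or Grade 2 anorexia with no more than Grade 1 weight loss.*
- **Stop selinexor:** *Any Grade ≥2 weight loss, or any Grade ≥3 anorexia.*

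Against the 15 pairs, the maintain row then holds 4: (0,1), (1,1), (2,1) and (2,0). The stop row holds 10, and none falls in both. Only grade 1 anorexia alone is unlisted, and the table's row for other events of grade 1 or 2 keeps the dose for it. No pair moves from stop to maintain.

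The rewrite does more than remove the overlap. It makes (3,1) an explicit stop, where 8 of 16 readings now give maintain only. It does the same for (2,3), which is maintain only when the maintain row takes reading (ii) or (iii) and the stop row takes (i), (ii) or (iv): 2 × 3 = 6 of 16. A line saying that the stricter row governs would settle (2,2), but would leave those maintain-only readings in place.

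The cost is a wording amendment to two rows, with no change to sample size, visits or the DLT definition. A few patients may stop selinexor who might otherwise have continued.
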